Official Study Title: Investigating the Cardiovascular Toxicity of Exposure to Electronic Hookah Smoking

Document Title: Study Protocol

NCT Number: 03690427

Document Date: Original IRB Approval Date November 6, 2018

Study Protocols for Vaping and Smoking Exposure Sessions:

E-Hookah Vaping Protocol. To determine the acute effect of e-hookah vaping on FMD, blood pressure, heart rate, and FMD were measured before and after (within ≤10 minutes) 30 minutes of e-hookah bowl vaping. Ten minutes after FMD testing (to allow arterial diameter to return to baseline size), endothelium-independent dilatation was assessed by administering sublingual nitroglycerin. Using an e-hookah bowl (Starbuzz Wireless E-head) placed on a traditional waterpipe, subjects were instructed to vape e-hookah fruit-flavored liquid containing 50/50 blend of propylene glycol and vegetable glycerin and 6 mg/mL nicotine, according to the package label (Starbuzz Tobacco, Inc.).

Traditional Charcoal-Heated Hookah Smoking Protocol. A traditional water-pipe was used for hookah smoking protocol. Participants were instructed to smoke the most popular brand of maassel cited by hookah smokers and manufactured in the United States (5%-10% tobacco fermented with molasses, fruit, and glycerin; Starbuzz Tobacco, Inc.) heated with two charcoal briquettes (Coco Nara 100% Natural Coal, Coco Nara).

To mitigate the impact of carryover effects, both exposure sessions were separated by a minimum of a 7-day washout period. Topography were standardized in accordance with hookah smoking puffing parameters observed in natural settings. Thus, for the duration of the 30-min inhalation sessions, all participants were cued verbally to inhale a 3-s puff at 20-s intervals, with vapor remaining in the lungs for approximately 3 s of breath-holding after inhalation. Supervision was carried out to prevent superficial vaping or hyperventilation. Experimental sessions took place in a specifically designed

smoking/vaping area, housed within the University of California, Los Angeles, Clinical and Translational Research Center.

Study Protocol for Flow-Mediated Dilation and Vascular Endothelium-Independent Dilation

Brachial artery flow-mediated dilation (FMD) was performed in strict accordance with guidelines described by Thijssen et al. *European Heart Journal*. 2019. Briefly, after a resting period of 15 minutes, the left arm was abducted at heart level, placed on a foam pad, and the brachial artery (3–7 cm above the antecubital crease) was imaged using a 5-to-12-MHz linear array transducer attached to a high-resolution ultrasound machine (Toshiba, Xario XG 2000). To ensure the location of the same arterial segment after the exposure session, anatomical landmarks were noted and the distance from the antecubital crease was recorded. A rapid-inflation/deflation pneumatic cuff (Hokanson) was placed on the upper forearm for 5 minutes and inflated to suprasystolic pressure (250 mm Hg). Doppler velocity was measured continuously with a fixed insonation angle of 60°, using a stereotaxic instrument to stabilize probe position.

Baseline diameter and velocity were recorded for 45 seconds and resumed 30 seconds before cuff deflation and continuously for 2 minutes after deflation to obtain true peak vasodilatory response. Recordings were triggered and captured at the R-wave of the ECG (end-diastolic diameter) using AccuSync 72 ECG trigger monitor and stored for offline analysis using validated edge-detection software (Brachial Analyzer for Research, Medical Imaging Applications, LLC). FMD measurements were calculated as absolute and percent changes in brachial artery diameter. Time to peak was calculated as the interval from the point of occlusion cuff deflation to the maximum brachial artery diameter. Peak hyperemic shear rate was calculated as (8× time averaged peak velocity)/occlusion diameter, based on a wide-centered sample volume from the first 15

velocity envelopes following cuff release. Because the main stimulus for FMD is an acute increase in hyperemic shear stress, to account for potential differences in peak hyperemic shear rate between conditions, FMD values were also normalized for the magnitude of the hyperemic stimulus (i.e., change in diameter divided by the hyperemic shear rate).

Vascular endothelium-independent dilatation was assessed with sublingual nitroglycerin (0.15 mg) with brachial artery images recorded continuously for 10 minutes. Since hormonal changes can affect FMD, women were studied in a standardized phase of the menstrual cycle (i.e., follicular phase).

Study Protocol for Intravenous Ascorbic Acid Protocol. To determine if oxidative stress plays a mechanistic role in the e-hookah vaping-associated decline in FMD, the acute effects of e-hookah vaping on FMD and exposure biomarkers were assessed before and after intravenous administration of a supra-physiological dose of ascorbic acid (Mylan Institutional Inc.): priming bolus of 0.06 g per kg fat-free mass dissolved in 100 mL of saline infused at 5 mL min⁻¹ for 20 minutes followed by an intravenous infusion of 0.02 g per kg fat-free mass dissolved in 30 mL of saline administered over 60 minutes at 0.5 mL min⁻¹. The maximum dose of ascorbic acid administered did not exceed 5 g. Ten minutes after FMD testing, endothelium-independent dilatation was assessed by administering sublingual nitroglycerin (0.15 mg) with brachial artery images recorded continuously for 10 minutes.

Study Protocol for Central Arterial Stiffness

Carotid-femoral PWV was measured by simultaneous waveform capture using both a thigh-specific cuff and carotid artery applanation tonometry (SphygmoCor XCEL; AtCor Medical). Velocity ($dsf - dsc$ (m) / time (s)) was calculated by measuring the time difference between the initial upstroke of the recorded waveforms at each site. The linear distance was measured manually from the suprasternal notch to the top of the thigh cuff at the center line of the leg, at the location of the femoral artery (dsf), and subtracting the distance from the suprasternal notch to the location of the carotid pulse (dsc). The transit time between the carotid and the femoral pulse waves was determined automatically by the SphygmoCor software.

The augmentation index was derived from the contour of the brachial BP waveform. The brachial-artery waveform, calibrated using oscillometric brachial artery BP, was analyzed by the validated brachial-to-aortic SphygmoCor transfer function to generate a central waveform and associated parameters. The augmentation index was calculated as the ratio of augmentation pressure (difference between the second and first systolic peaks of the aortic pressure waveform) and pulse pressure expressed as a percentage.

Study Protocol for Biomarkers of Oxidative Stress and Inflammation

Blood samples were obtained from the antecubital vein, drawn into pre-iced heparinized vacutainers, and placed on ice. Tubes were sent to the University of California, Los Angeles, Clinical Laboratory for inflammatory biomarker analyses, which were performed within 24 h after collection. One tube was centrifuged to separate plasma for antioxidant biomarker analyses, and samples were frozen at -80°C in a cryopreservative solution.

Arylesterase Activity: Activity was determined by the rate of hydrolysis of phenyl acetate to phenol. Briefly, 4 mL plasma was incubated with 3.5 mM phenyl acetate in 9 mM Tris-HCl buffer (pH, 8.0) containing 0.9 mM CaCl₂ at RT. The kinetics of phenol formation were determined by recording the absorbance at 270 nm every 15 s for 2 min. The activity was expressed as nanomoles of product formed per minute per milliliter of plasma.

PON-1 Activity: The ability of PON-1, associated with HDL, to hydrolyze paraoxon substrate was determined. The hydrolysis of paraoxon (diethyl-p-nitrophenyl phosphate) to p-nitrophenol by PON-1 was determined by incubating 5 mL of plasma with 1.0 mM paraoxon in 100 mM tris-HCl buffer (pH, 8.5). The kinetics of p-nitrophenol formation was determined by recording absorbance at 405 nm every 15 s for 4 min. The enzyme activity was expressed as micromoles of p-nitrophenol formed per minute for every 1 mL plasma and assayed in triplicates. The intra-assay CV for the assay was 2.60% and the interassay CV was 8.95%.

HDL Antioxidant Capacity: Capacity was determined as the ability of HDL to inhibit LDL-induced oxidation of dihydrodichlorofluorescein into the fluorescent dichlorofluorescein.

Capacity was expressed as an HDL oxidative index, determined by the ratio of dichlorofluorescein fluorescence in the presence and absence of HDL and assayed in triplicates. An index of < 1.0 denotes protective antioxidant HDL, whereas an index of > 1.0 indicates pro-oxidant HDL. The within-assay CV was 6.89%. The interassay CV for four separate measurements over a period of 2 months was 7.30%.

Serum hsCRP levels were analyzed using the immunoturbidimetric method using the Siemens Vista Dimension analyzer, which provides a minimum detection level of < 0.2 mg/L; and TNF α was analyzed using quantitative multiplex bead assay.

Biomarkers of Exposure. Plasma nicotine levels were assayed by gas chromatography with nitrogen-phosphorus detection, using 5-methylnicotine and 1-methyl-5-(2-pyridyl)-pyrrolidin-2-one (ortho-cotinine) as internal standards. Expired carbon monoxide (CO) measurements were carried out using a CO meter (Micro Smokerlyzer; Bedfont Scientific Ltd.).

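### Do the 15-minute rest, the 10-minute post-vaping window and the untimed ascorbic acid session undermine the FMD comparisons?

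*Protocol*

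**What the plan says.** The E-Hookah Vaping Protocol fixes the measurements around the exposure: "blood pressure, heart rate, and FMD were measured before and after (within ≤10 minutes) 30 minutes of e-hookah bowl vaping". The nitroglycerin test comes later: "Ten minutes after FMD testing (to allow arterial diameter to return to baseline size".

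The protocol's section on flow-mediated dilation describes the scan once, for all occasions. Imaging starts "after a resting period of 15 minutes, the left arm was abducted at heart level". The cuff "was placed on the upper forearm for 5 minutes and inflated to suprasystolic pressure". On recording: "Baseline diameter and velocity were recorded for 45 seconds and resumed 30 seconds before cuff deflation and continuously for 2 minutes after deflation". The section presents itself as a short account of a published guideline. It mentions finding the same arterial segment again after exposure, but does not mention rest before that second scan.

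The ascorbic acid section states its aim as "To determine if oxidative stress plays a mechanistic role in the e-hookah vaping-associated decline in FMD", and says that "the acute effects of e-hookah vaping on FMD and exposure biomarkers were assessed before and after intravenous administration". The priming dose runs "for 20 minutes followed by an intravenous infusion" of 60 minutes. Neither the vaping nor the FMD scans are given a time relative to these two stages.

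The SAP section on endothelial function tests pre-to-post changes within participants, and then compares the change in the ascorbic acid session with the change in the e-hookah session. Both use paired tests. It does not define the pre measurement for the ascorbic acid session.

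**The concern.** Two things look wrong.

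First, a 15-minute rest and a 10-minute window do not fit together if the rest is taken in full after vaping. If the rest was dropped for the second scan, the paired scans were made under different resting conditions. The pre-to-post change may then contain a rest effect as well as a vaping effect.

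Second, the mechanistic question depends on where the pre scan falls in the ascorbic acid session. If it came before the agent and the post scan after it, the session's change would include what ascorbic acid does to FMD by itself. The two sessions could then differ even if ascorbic acid left the vaping effect untouched, and the result could be misread as evidence about oxidative stress.

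**Working it through.** **Inputs.** From the E-Hookah Vaping Protocol: vaping 30 min, window 10 min. From the FMD section: rest 15 min, baseline recording 45 s, occlusion 5 min, recording after deflation 2 min. From the ascorbic acid section: 100 mL at 5 mL/min, then 30 mL at 0.5 mL/min.

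**1. Administration time.** 100 / 5 = 20 min and 30 / 0.5 = 60 min, matching the durations printed in the protocol. Their sum, 80 min, is not printed.

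**2. Scan length.** 0.75 + 5 + 2 = 7.75 min. The 30 s recorded before deflation lies inside the occlusion.

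**3. Rest against window.**
- If the window limits the start of the scan, it ends by 10 + 7.75 = 17.75 min after vaping.
- If the window limits completion, 10 - 7.75 = 2.25 min remain for positioning, blood pressure and heart rate.
- With a full rest after vaping, the scan starts at 15 min, which is 15 - 10 = 5 min late, and ends at 15 + 7.75 = 22.75 min. This fits neither meaning of the window.

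Two readings avoid the conflict: the rest applied only before the first scan, or part of the vaping period counted towards it.

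**4. Spacing from end of pre scan to start of post scan.** Assume no other delays (including no nitroglycerin test between the pre scan and vaping), the window limiting scan start, and the same window in both sessions. The e-hookah session gives 30 + (0 to 10) = 30 to 40 min. For the ascorbic acid session, three example placements are:

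| Pre scan and vaping | Spacing (min) | Difference from e-hookah session (min) |
|---|---|---|
| Pre scan under ascorbic acid, directly before vaping | 30 to 40 | 30 - 40 = -10, to 40 - 30 = +10 |
| Pre scan before the bolus, vaping after the bolus | 50 to 60 | 50 - 40 = 10, to 60 - 30 = 30 |
| Pre scan before the bolus, vaping after the full administration | 110 to 120 | 110 - 40 = 70, to 120 - 30 = 90 |

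If the window limits completion, the e-hookah spacing is 30 to 32.25 min and the differences narrow to -2.25 to +2.25, 17.75 to 22.25 and 77.75 to 82.25 min. Single values of 0, 20 and 80 min would need identical delays in both sessions. Other placements, such as vaping during the bolus, would give other figures.

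**5. What the comparison estimates.** Let v be the vaping effect, i the change in v due to ascorbic acid, a the agent's own effect on FMD, and r1, r2 the rest and time effects in the e-hookah and ascorbic acid sessions.
- E-hookah change: v + r1.
- Ascorbic acid change, both scans under the agent with a constant: v + i + r2. Difference: i + (r2 - r1).
- Ascorbic acid change, pre scan before the agent: v + i + a + r2. Difference: i + a + (r2 - r1).

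The worry therefore rests on the term a, which spacing in minutes does not measure. Equal rest and timing effects cancel (r1 = r2) in the between-session comparison, though r1 stays in the single-session pre-to-post test.

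**6. Which design the text supports.** The thing assessed before and after ascorbic acid is the acute effect of vaping on FMD. In the E-Hookah Vaping Protocol that effect is itself a before-and-after-vaping change. Read this way, one such change was obtained without the agent and one with it, and a largely drops out. The stated aim concerns the decline linked to vaping, which fits. The SAP's within-participant test is likewise anchored to exposure. Only its description of the session change as due to ascorbic acid is looser.

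**The case for a change.** The strongest reply is that the text never settles the matter. The timing phrase in the ascorbic acid section can be read as placing one scan on each side of the administration, and the SAP's loose description of the change allows this. On that design, the difference i + a + (r2 - r1) can be non-zero with i = 0. The cited guideline may cover rest, but it could not place this trial's vaping on this trial's infusion timeline. Neither nitroglycerin nor shear normalisation shows where the pre scan lay. Clarifying would cost only a few sentences.

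Much of this stands. The omissions are real, and a full rest after vaping cannot be squared with the window. A reader cannot confirm the timing from these documents.

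It does not establish a fault in the plan. The harmful design is possible but not shown to have been used, and it is the less natural reading. Every remedy would be to state, define or report something, and most would apply only if a particular design turned out to be the one used. None replaces a stated method with a better one. The effect of unequal rest is also partly contained: each scan has its own 45-second baseline, and FMD is also normalised for the hyperemic stimulus. The nitroglycerin test adds only a partial check, since it comes ten minutes after FMD.

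**Conclusion.** No change to the plan follows. This is a gap in description that people holding the session records can fill. The text is in the past tense, so the order of scans, vaping and infusion is already a matter of record.

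On rest, an early post-exposure scan is a fair trade-off. It measures the acute effect soon after exposure, at the price of possibly unequal rest, and a full rest after vaping would move the scan at least 5 minutes outside the stated window. Whether the window limits the start or the completion of the scan shifts an upper limit by 7.75 minutes, with no shown consequence for any conclusion.

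On ascorbic acid, the natural reading makes the paired comparison estimate the change in the vaping effect, apart from any difference in rest and timing. Pre-to-post spacing then differs between sessions by -10 to +10 minutes, if both used the same window, the window limits scan start and there were no other delays.

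The conclusion rests on that reading and on ascorbic acid's own effect being roughly constant across the two scans. If the records showed the pre scan before the agent and the post scan after it, the mechanistic statement would have to be limited accordingly. That is a matter of interpretation at reporting, and the paired tests would stay the same. No FMD values are given, so no bias can be sized or signed.

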Official Study Title: Investigating the Cardiovascular Toxicity of Exposure to Electronic Hookah Smoking

Document Title: Statistical Analysis Plan

NCT Number: 03690427

Document Date: Original IRB Approval Date November 6, 2018

Statistical Analysis Plan for Endothelial Function

Statistical analyses were performed using SAS (version 9.4). Data were analyzed by the Shapiro–Wilk test to determine distribution. Once normality was demonstrated, we tested within-participant pre- versus post-exposure changes using paired t tests. For non-normally distributed variables Wilcoxon signed-rank test was used. We applied paired t tests to compare the pre- versus post-changes induced by ascorbic acid versus e-hookah vaping for variables that were normally distributed, and Wilcoxon signed-rank test for non-normally distributed variables. Data are expressed as mean \pm SE. Data for plasma nicotine, exhaled carbon monoxide, and flow-mediated dilation normalized for shear were not normally distributed and were additionally expressed as median (interquartile range). Statistical significance was set at the 0.05 level.

Statistical Analysis Plan for Central Arterial Stiffness and Biomarkers of Oxidative Stress and Inflammation

Paired Student *t* tests were used to compare continuous variables between sessions before and after exposure. Because of the crossover study design, we used a general linear model approach for repeated measures to examine differences between e-hookah and traditional combustible hookah; the models included two within-subject factors (product type and time point relative to exposure session), and the sequence of type of product exposure was included as a between-group factor. The effect of primary interest was the interaction between the two within-subject factors, product type and time point relative to the exposure session. Effect sizes are for the interaction of product-by-time point relative to exposure in the general linear model repeated-measures analysis and translated from eta-square metric to d-metric. Statistical significance was set at 0.05 and analyses were conducted using SPSS Statistics version 24.0 software (IBM).

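### The augmentation index is analysed as a stiffness measure with no account of heart rate, so a heart-rate rise after exposure would lower it even if the artery were unchanged

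*Protocol*

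**What the plan says.** The Protocol section on central arterial stiffness names two measures, carotid-femoral pulse wave velocity and the augmentation index. For the index, the brachial waveform "was analyzed by the validated brachial-to-aortic SphygmoCor transfer function to generate a central waveform and associated parameters". The definition follows: "The augmentation index was calculated as the ratio of augmentation pressure (difference between the second and first systolic peaks of the aortic pressure waveform". The denominator is pulse pressure, and the result is given in percent. It contains no heart-rate term and no reference rate.

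The SAP section on stiffness and biomarkers uses paired t tests for before-and-after comparisons. It compares the products with a repeated-measures general linear model: "the models included two within-subject factors (product type and time point relative to exposure session", with exposure sequence as a between-group factor. The product-by-time interaction is named as the main interest. Heart rate is not in the model, and no sensitivity analysis is planned.

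Heart rate is nevertheless recorded in at least part of the study. The e-hookah protocol states that "blood pressure, heart rate, and FMD were measured before and after (within ≤10 minutes) 30 minutes of e-hookah bowl vaping". The e-liquid contains "6 mg/mL nicotine, according to the package label". The comparator is described as "5%-10% tobacco fermented with molasses, fruit, and glycerin", and its nicotine content is not stated.

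**The concern.** The numerator of the index is the second systolic peak minus the first. The second peak depends on where the reflected wave lands within ejection. When the heart beats faster, ejection is shorter, so a wave with an unchanged return time lands relatively later and adds less. The same artery then yields a lower index.

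The pre-post change in the raw index therefore mixes any change in stiffness or wave reflection with a heart-rate component of opposite sign when heart rate rises. A true increase after exposure could be reduced, cancelled or reversed. If one product raised heart rate more than the other, that product would look less harmful on this measure. In a toxicity study that is the unwelcome direction.

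The plan accepts this kind of reasoning elsewhere. The flow-mediated dilation section adds a version of that outcome normalised for its shear stimulus and keeps the unnormalised one. The augmentation index has no such companion.

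**Working it through.** The documents give no heart-rate response, index value, slope, SD or sample size, so there is no figure of the plan's own to reproduce. The text settles the omission. The arithmetic below only illustrates its size.

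**Step 1: is heart rate used anywhere?** The index definition is augmentation pressure over pulse pressure. The model terms are product, time and sequence. Neither contains heart rate. The one statement that heart rate was measured, "blood pressure, heart rate, and FMD were measured before and after", belongs to the e-hookah vascular protocol and is not linked to the index.

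**Step 2: direction.** Assume ejection lasts 413 ms minus 1.7 ms per bpm, and the reflected wave returns at a fixed 140 ms.
- At 65 bpm: 413 - 1.7 × 65 = 302.5 ms; 140/302.5 = 46% of ejection.
- At 75 bpm: 413 - 1.7 × 75 = 285.5 ms; 140/285.5 = 49% of ejection.

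The wave arrives relatively later although nothing in the artery has changed. A simple model using this ejection formula, one reflected wave (coefficient 0.45) and a reservoir term gives falls in the index between 65 and 75 bpm of 3.6 points (return time 120 ms), 5.7 (140 ms) and 7.2 (160 ms). Its settings are assumptions. It supports the sign and the order of size, no more.

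**Step 3: size.** Let s be the assumed fall in the index per bpm: 0.2, 0.4 or 0.5 points, that is 2, 4 or 5 points per 10 bpm. Let ΔHR be the pre-post change in heart rate.

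Within-product bias = -s × ΔHR:

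| ΔHR (bpm) | s = 0.2 | s = 0.4 | s = 0.5 |
|---|---|---|---|
| 0 | 0 | 0 | 0 |
| 5 | -1.0 | -2.0 | -2.5 |
| 10 | -2.0 | -4.0 | -5.0 |
| 15 | -3.0 | -6.0 | -7.5 |

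Bias in the interaction = -s × (ΔHR with e-hookah - ΔHR with traditional hookah), taking the same s for both products. With equal responses it is 0. With responses 5 bpm apart its size is 5 × 0.2 = 1.0 to 5 × 0.5 = 2.5 points, and the product with the larger rise appears more favourable.

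**Step 4: effect on a paired test.** Assume an SD of change of 8 points and a two-sided test at 0.05 (the SAP gives the level but not the sidedness). The noncentrality is (bias/SD) × √n; for 4 points and n = 20 it is (4/8) × √20 = 2.24.

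| Net shift (points) | n = 12 | n = 20 | n = 30 |
|---|---|---|---|
| 4 | 35% | 57% | 75% |
| 2 | 12% | 19% | 26% |
| 0 | 5% | 5% | 5% |

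A pure 4-point artefact would be declared significant at the rates in the first row. Those rates are also the power for a true rise of 4 points. An artefact of -2 cuts that power to the second row, and an artefact of -4 cuts it to the third.

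**The case against.** The strongest reply is that nothing in the documents shows the bias to be material. No heart-rate change is reported, every size above is assumed, and the documents do not say when the index was read relative to exposure; the 10-minute window is attached to blood pressure, heart rate and flow-mediated dilation. All of this stands, and it limits the point to a possibility.

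The second reply is that the main contrast is protected. A heart-rate response common to both products cancels in the interaction at a common slope, and session length, puff duration, puff interval and breath-holding are standardised. This stands in part. Standard puffing does not establish equal nicotine delivery, so different heart-rate responses remain possible. A reader might infer that the product comparison is biased as planned; the documents do not support that, because they show no difference in heart-rate response.

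The third reply is that the raw index is a clearly defined total-effect measure and that heart rate is itself changed by exposure. Adjusting for it can introduce new error where heart rate and wave reflection share causes. This also stands. A reader might infer that only a heart-rate-standardised result may be interpreted, which goes too far. The standardised index depends on its slope, and in the wave model that slope ranges from 3.6 to 7.2 points per 10 bpm with return time, so one fixed correction can over- or under-correct.

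Finally, the documents are written in the past tense, so any addition may be post hoc. That affects how it is labelled, not whether it is useful.

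**Conclusion.** The concern holds in a limited form. The plan labels the raw augmentation index a measure of central arterial stiffness but offers no means of separating a stiffness effect from a heart-rate effect after a nicotine-containing exposure. The within-product pre-post comparison is exposed to any heart-rate change: -2 to -5 points for a 10 bpm rise at the assumed slope of 2 to 5 points per 10 bpm. The product-by-time interaction is exposed only if the products differ in heart-rate response: 1.0 to 2.5 points for a 5 bpm difference, and nothing if the responses are equal and the slope is common. The direction follows from the definition of the index at fixed reflection time; the sizes rest wholly on assumption.

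A reader might extend this to all the stiffness results. That is not supported: carotid-femoral pulse wave velocity is calculated from distance and transit time, does not use this ratio, and is outside this point.

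**What to change.** - Keep the raw index as defined and describe it as the total effect.
- As a sensitivity analysis, standardise each reading to a fixed reference heart rate (for example 75 bpm), using the heart rate from the same waveform in both sessions. Run the same paired tests and the same product-by-time model with sequence. State the slope used and where it comes from.
- A model with heart rate as a time-varying covariate is an alternative. It is not equivalent, because it estimates the slope from these data instead of imposing one. Choose one in advance, or report both as different analyses.
- Report the pre-post change in heart rate for each product.
- State that when raw and standardised results disagree, a change or lack of change in the raw index will not be attributed to stiffness.
- State that heart rate was captured with every index reading in both sessions; at present its measurement is explicit only for the e-hookah vascular protocol. If results have already been seen, label the analysis post hoc.

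The cost is SAP wording and one derived variable. If the stored recordings carry heart rate, as expected of pulse waveforms, no new participant or measurement is needed. The downside is interpretive: exposure affects heart rate, so the standardised result is the effect not explained by heart rate, depends on the assumed or estimated slope, and must be labelled as such.
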